## 5.4 Inclusion/Exclusion Criteria

### **VA Patients**

Inclusion criteria are reflective of the criteria to participate in SMAs and P2P, with the addition of criteria to insure informed consent:

1. Meet at least one of the following criteria in the past 2 years:  
For data pull patients:
  - a. At least one VA hospitalization with a type 2 diabetes-related ICD-9 or 10 code
  - b. At least two VA outpatient visits with a type 2 diabetes-related ICD-9 or 10 code, or
  - c. At least one VA prescription for a glucose control medication (insulin or oral agents) or monitoring supplies.  
For clinical referrals:
  - a. Scheduled for diabetes SMA
2. Poor glycemic control, indicated by a HbA1c in the past six months of:
  - a. at least 7.5% if age < 70, or
  - b. at least 8% if age 70+
3. No active substance abuse disorder (smoking cigarettes is not an exclusion)
4. No serious psychiatric illness, including bipolar disorder, dementia, schizophrenia, or personality disorders (MDD and PTSD are not exclusions)
5. Has a current address and telephone number listed in VA databases
6. Is competent to provide informed consent
7. Can communicate in English and by telephone
8. Not terminally ill
9. Able to participate in an outpatient program
10. Not a prisoner

### **VA Employees**

VA Employees will be asked to participate based on their role in the SMA and/or P2P programs. The director of primary care, clinicians participating in the SMAs, P2P group facilitators, and other key staff involved in diabetes patient care (e.g., nurses, dieticians, pharmacists) will be asked to participate in the pre-, mid-, and post-implementation semi-structured interviews. For the sustainment assessment, members of Ann Arbor teamlets who are involved in upcoming SMAs (e.g., MD, PharmD, RD, RN, LPN, MSA, etc.) will be asked to participate.

## 5.5 Study Evaluations

### **Patient Research Participants**

VA patient research procedures include completion of three surveys (baseline, 6 months post enrollment, and 12 months post enrollment) and collection of medical record data from VA databases. Additionally, a subset of participants will be asked to participate in interviews as part of the program evaluation.

### **Patient Inactive Controls**

Medical record information will be pulled from VA databases. The data will include A1c levels, blood pressures, insulin start dates, statin use, and number of admissions/bed days of care/outpatient visits.

### **Patient Refusers of SMAs and P2P**

Patients in the declined participation group will be asked to answer a few questions by the RC at the time of refusal or soon after refusal by telephone.

### **Employee Research Participants**

Semi-structured interviews with five to eight key informants (VA staff) at the participating sites will be conducted to obtain information on CFIR constructs likely to influence implementation success. These interviews will include the director of primary care, clinicians participating in the SMAs, the P2P group facilitators, and other key staff involved in diabetes patient care (e.g., nurses, dieticians, pharmacists). Additionally, in Ann Arbor, up to an additional 25 VA employees will participate in sustainment assessments (i.e., interviews, meeting observations, SMA observations). These employees will include all members of the teamlets involved in hosting upcoming SMAs.

## **5.6 Data Analysis**

This will be an effectiveness trial conducted under real-world implementation conditions in multiple sites and regions. The focus is on assessing the impacts of the P2P program on patient outcomes as well as optimization of the implementation strategy.

### **5.6.1 Analysis Plans by Aim**

Aim 1 (Evaluation of the effect of SMAs and SMAs+P2P compared to usual care on diabetes patients' glycemic control, blood pressure, statin use, and insulin starts at 6 and 12-18 months post-enrollment): The primary analysis will be an intention to treat analysis (ITT) comparing all participants scheduled for an SMA (regardless of whether an SMA was actually attended) and eligible patients randomized to usual care. We also will conduct analyses comparing outcomes between the usual care group and: 1) The SMA Attendee group, defined as a subset of those in the SMA ITT group who attended at least one SMA; and 2) the SMA Engagement group, defined as the subset of patients who attended at least half of the SMAs offered in the series.

We will conduct a "difference-in-differences" (DID) analysis on our primary A1c outcome using a multilevel linear mixed effect model. The model will include an indicator of treatment, an indicator for time, the treatment-time interaction (DID estimator), and variables to adjust for baseline A1c, age, gender, and race. Random intercepts to include will be for patients (level-1) nested within site (level-2). An identical analysis will be used for the secondary SBP outcome. In the secondary analyses of insulin and statin starts, we will implement a multilevel logistic regression model, and for anti-hypertensive medication class changes, we will implement a multilevel Poisson regression model. To analyze the 6- and 12-month differences in utilization measures between treatment groups, we will use a two-sample Mann-Whitney U test. Vargha and Delaney's A statistic will be used to describe the effect size of the Mann-Whitney test. As a robustness check, we will repeat the above analyses on a subset of patients who will be matched 1:1 based on propensity scores. The propensity score model will be developed using a logistic regression on the patient demographics. Although our initial analyses will use observed data, because we are relying on data available in the EHR, we anticipate more missing values than if this were an efficacy trial. Accordingly, we will use logistic regression to model patients' likelihood of having outcome data and defined strata within which outcome values were missing at random. We will then stratify patients according to these propensities and randomly sample from the observed outcome distribution and impute these values for missing data within each stratum. As a sensitivity analysis for the primary A1c outcome, we will impute the missing data such that any missing A1c measurements at 6 or 12 months will match the value at baseline.

Aim 2 (Assessment of the impact of SMAs and SMAs+P2P on service utilization and patient-centered outcomes, including patients' satisfaction with VA care, diabetes-specific quality of life and social support at 6 and 12 months post-enrollment). In our analysis of changes in patient-centered outcomes as reported on patient surveys, we will conduct a paired Wilcoxon signed rank test to determine if there are significant changes between baseline and the 6- and 12-month post-enrollment evaluation periods. We will use the Benjamini-Hochberg (BH) procedure to attempt to control the false discovery rate due to the multiple comparisons. There were very few participants in the SMA+P2P group chose to be formally matched with another participant in their SMA to give and receive peer support outside the SMA. If we do not have sufficient sample size of participants in P2P, we will be unable to compare outcomes between the SMA-only and SMA+P2P arms. In that case, will only conduct our primary analysis that combines the two SMA groups (SMA-only and SMA+P2P) into one active treatment group and compare clinical outcomes of participants participating in SMAs with those in usual care.

Fidelity of the P2P Program. To collect data on fidelity, checklists of key content areas to cover and communication skills that should be used will be completed and forwarded to Ann Arbor. A HBC or another qualified health behaviorist will attend the first P2P visit (immediately following the first SMA) and will complete a fidelity assessment checklist. Additionally, they will provide feedback to the P2P facilitator immediately following the session. This feedback will be documented and shared with the Ann Arbor study team. An assessor will continue to attend drop-in sessions, completing fidelity assessments and providing feedback, until he/she feels the P2P facilitator is ready to continue without assistance. Then the fidelity assessments will be completed approximately every 3rd drop-in session for the remainder of the study. Additionally, the P2P facilitators will be asked to complete self-assessment checklists after each session which will be forwarded to Ann Arbor.

Process and Content Assessments of SMAs. A fidelity checklist of key content areas to cover and communication skills that should be used will be completed and forwarded to Ann Arbor. The intention of this assessment is for us to keep track of what is being covered during the SMAs, but we will not provide feedback to the facilitators. The goal is for the local sites to maintain local control over the content of their SMAs. The HBC or RC will attend all sessions of first and last SMA cohorts during the study period (and one in the middle if possible) and any cohorts following a significant change in SMA curriculum/protocol. A SMA facilitator will be asked to conduct a self-assessment at all sessions, which are also to be forwarded to Ann Arbor.

Aim 3: Staff interviews will be used to identify recommendations and develop a tool-kit for facilitating widespread dissemination efforts, and to contribute to the implementation science literature. The evaluation will include semi-structured interviews with five to eight key informants at the participating sites, including the director of primary care, clinicians participating in the SMAs, P2P group facilitators, and other key staff involved in diabetes patient care (e.g., nurses, dieticians, pharmacists). During the start-up period of this project, key stakeholders helped identify a subset of CFIR constructs that are likely to play a role in the effectiveness of the P2P program, such as: relative advantage, adaptability, complexity, and cost (intervention characteristics); patient needs and resources, external policies and incentives (outer setting); networks and communications, relative priority, goals and feedback, leadership engagement, available resources (inner setting); knowledge and beliefs (characteristics of individuals); and planning and engaging (process). These relevant constructs will be used to develop the semi-structured interview guides and to deductively code the interview responses. Interviews will be audiotaped and transcribed. Seven to ten months and eighteen months to two years following implementation of the SMA + P2P program at the participating sites, we will use this data collection procedure for collecting data on CFIR constructs from staff at the participating sites.

Additionally, in Ann Arbor, semi-structured interviews, meeting observations, and SMA observations will be conducted to further evaluate clinical efforts to sustain SMAs. The evaluation will include all members of teamlets involved in upcoming SMAs. The interviews will be audiotaped and transcribed. Teamlet planning meetings and SMAs will be observed by two

members of the Ann Arbor study team, who will take detailed notes. The notes from the SMA observations will not include any patient data, but will rather focus on how the SMA is structured and how the facilitators run the session.

In addition, we will conduct semi-structured interviews with a random sample of patients invited to participate in SMAs or SMAs + P2P, to better understand their experiences with the program (above and beyond their satisfaction with the program, determined as part of Aim 4). We will purposefully sample up to 140 Veterans, approximately 15-20 at each site (including of the four clinics within the Palo Alto site), approximately 12 months after enrollment, stratified into three groups according to level of participation in the intervention: low participation (began the intervention but completed fewer than 25% of weekly phone calls/group sessions in 12 months of program participation); moderate participation (completed approximately 50% of weekly phone calls/group sessions); and significant participation (completed greater than 75% of weekly phone calls/group sessions). By stratifying according to level of participation, we hope to understand both the barriers and facilitators patients experience in participating in the program. For the declined participation group, the RC at each site will ask patients who are contacted but do not enroll if they are willing to answer a few questions. These questions will be asked by the RC by phone at the time the patient declines participation in the SMA program. These questions will also be asked of those who participate in SMAs and are offered P2P as an optional add on but decline. The RC will ask these in person whenever possible; otherwise the RC will do this by phone. Those who agree to this short (expected to take less than 5 minutes) questionnaire will be asked questions about demographics, diabetes management and service utilization. The responses will be entered into a database, but there will be no patient identifiers. Interviews for the remaining groups will be conducted by telephone by Ann Arbor study staff and will last about 20 minutes. These interviews will be audio-recorded for transcription and analysis. We will continue to sample and interview patients until additional interviews no longer identify new themes in the areas of inquiry.

Analysis of the qualitative data from the formative evaluations will begin with a deductive approach to coding interview data according to CFIR constructs. Once the data have been organized by constructs, an ordinal value (-2, -1, 0, 1, or 2) will be assigned to each construct at each site. These values represent the perceived magnitude and “role” of each construct in the implementation of the program—e.g., -2 for the construct of “relative priority” means there are a number of other high priority clinical programs competing for resources/attention, +2 means the proposed program has a high priority compared to other programs based on explicit facility goals related to improving the care of patients with diabetes. The data will also be coded inductively, to identify themes or issues not captured by the CFIR constructs that may deserve attention during the implementation process. In the post-implementation evaluation these data will then be used to construct a matrix for identifying potential correlations between each construct and program outcomes. Strong correlations will then form the basis of specific recommendations for program dissemination.

Table 4 provides an example of what the matrix might look like for analyzing the staff interview data. Constructs A and B do not appear to be correlated to program outcomes, in that there is no orderly progression from low to high magnitude of the construct, consistent with the progression from small to large decrease in HbA1c. In contrast, constructs C and D do show a correlation, suggesting that these constructs might be important factors affecting successful implementation of the program. Thus, these findings can be used to develop recommendations for future efforts to disseminate the program, depending on what these factors are, and how they are manifested in the individual sites. We have used this rating process successfully to identify those constructs that appear to be most closely correlated with intervention outcomes in four different VA QUERI implementation studies, including an evaluation of VHA’s specialty care initiatives (E-consults and SCAN-ECHO). The process provides a more systematic means of linking constructs to implementation success than simply organizing qualitative data according to themes.

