treatments will be offered in a random sequence within site, providing the clusterized random assignment required for comparability of the two treatment arms. In a modification of the classical cluster randomized design, patients are not assigned to groups prior to the group randomization to treatment but are recruited from a population of eligible patients when the site is ready to run a new group. If patients are then selected differentially into the groups we will lose all the advantages of the randomization step. Thus patients will be randomly sampled for invitation from eligible patients and recruited for each wave of the group treatment with a standard script that is identical whether the group is SMA only or whether P2P will be offered as an additional optional part of the intervention. All invited patients will be told that they are being invited to participate in SMAs, provided a brief description of what the SMAs involve, and informed that some groups will also be offered an additional (optional) opportunity to participate in P2P as a supplement to the SMAs. All invited patients will also be told that they are being offered an additional (optional) opportunity to participate in this research study. Participation in the research study is not required to participate in the SMAs or SMAs + P2P.

The study population will consist of diabetes patients who have poor glycemic control. Because not all eligible patients will be able to be invited to participate in one of the two programs during the study period, we will also have a pool of eligible patients whom we can use for untreated controls. We will randomly pull a sample of patients from each site to serve in this group. Thus, the trial will compare outcomes across three different treatment groups: (1) usual care without SMAs, (2) SMAs; and (3) SMAs + P2P.

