#### **Existing Mechanisms**

During the start-up period of this project, many of the participating sites established a strong referral base and high participation rate in their SMAs. All patients referred to SMAs will be scheduled into the next available SMA; the scheduler will not be aware of which SMA groups will be offering P2P as an additional optional component. Once the patient is scheduled, the scheduler will communicate the patient's information to the RC through encrypted email, CPRS alert, or a phone call.

All patients scheduled for an SMA who meet our eligibility criteria will be mailed the Study Intro Letter, the Study Info Letter, a HIPAA authorization, and the baseline survey. Participants will be asked to return the baseline survey (with a waiver of written informed consent) prior to attending their first SMA, and the signed HIPAA authorization prior to the study team linking medical record data to the survey data. The RC may call participants who have not returned the baseline survey and/or HIPAA prior to the first SMA. Whenever possible, the RC will attend the first SMA in order to administer/collect any outstanding baseline surveys and/or HIPAAs for those interested in the study, and distribute incentives for completion. Depending upon what type of group is starting at the time the participants are starting SMAs, they will become part of the **SMA group** or the **SMA + P2P group**.

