#### **Data Pull**

Each quarter, the Data Manager will pull a list of all patients meeting the eligibility criteria outlined below. At our Ann Arbor site and Palo Alto site and subsites, the RC will provide

each newly eligible patient's assigned provider (PCP or RN) the opportunity to opt that patient out of SMA recruitment. Providers will be asked to respond within 1 week and at that point, any patients who were not opted-out will be recruited.

Eligible patients will be sent an SMA Info Letter explaining that they are being invited to participate in SMAs, provided a brief description of what the SMAs involve, and informed that some groups will also be offered an additional (optional) opportunity to participate in P2P as a supplement to the SMAs. This introductory letter will also explain that they will be asked if they are interested in participating in a research study to evaluate this program. It will explain that they may participate in the SMAs regardless of their decision to participate in the research study. It will also include a phone number to call to opt-out of the invitation to participate in the research study, or to opt-out of both the invitation to participate in SMAs and the research study. Unless patients respond that they do not wish to participate, the letters will be followed with a phone call to further describe the program. If patients are interested in participating, they will also be asked a set of brief screening questions to screen out people with active substance abuse. Then the RC will schedule the patient to attend an upcoming SMA or SMA + P2P meeting. Veterans who do not wish to participate will be replaced with another Veteran randomly selected from the population of eligible Veterans, until the SMA group is filled. A full group will range from 10 – 14 patients depending upon the site resources.

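### The primary SMA versus usual-care contrast is labelled as randomised and intention to treat, but random selection governs only invitation in one recruitment stream and is lost by the time patients are scheduled

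*Combined protocol and SAP*

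**What the plan says.** **What is randomised.** Section 5.1.1 randomises the within-site order of SMA and SMA+P2P groups, "providing the clusterized random assignment required for comparability of the two treatment arms". The two arms meant are SMA and SMA+P2P.

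**How patients reach the SMA side (Section 5.2).** There are two streams.
- Existing Mechanisms: "All patients referred to SMAs will be scheduled into the next available SMA". The section adds that "many of the participating sites established a strong referral base and high participation rate in their SMAs". Under Section 5.4 these patients enter on "Scheduled for diabetes SMA" in place of the diagnosis and prescription criteria.
- Data Pull: invitations are a random sample of eligible patients. At Ann Arbor and at Palo Alto with its subsites, the provider first has "the opportunity to opt that patient out of SMA recruitment". Interested patients then pass a telephone screen for substance abuse. "Veterans who do not wish to participate will be replaced with another Veteran randomly selected from the population of eligible Veterans".

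In both streams, research participation is a further choice, and a signed HIPAA authorization is needed before record data are linked to surveys (Sections 5.2 and 5.3).

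**Controls.** Section 5.1.1 draws them at random from patients who were not invited. Section 5.2 draws them from patients whom chance left uninvited. Section 5.3 says that they are not contacted.

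**Analysis (Section 5.6.1).** The primary analysis is called intention to treat, "comparing all participants scheduled for an SMA (regardless of whether an SMA was actually attended) and eligible patients randomized to usual care". The A1c model has treatment, time and their interaction, with baseline A1c, age, gender and race as adjusters. A robustness check matches 1:1 on a propensity score built from demographics. Under Aim 2, the plan says that very few SMA+P2P patients chose formal peer matching, and that SMA versus SMA+P2P may not be compared at all.

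**The concern.** An intention-to-treat analysis keeps patients in the groups to which chance assigned them. Here one side is defined by scheduling, which follows referral or acceptance, and the other by sampling from records. Referral and willingness to join are therefore part of the contrast.

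If SMA versus SMA+P2P is dropped, the comparison that rests on the random sequence disappears. What remains is scheduled patients against usual care, plus the attendee and engagement subsets against the same controls. The main clinical conclusion would then be reported as a randomised result without a randomised basis. The planned adjustment also matters more than it would in a randomised trial, so it is worth asking what it can correct.

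**Working it through.** **1. Steps on each side, from Sections 5.1.1, 5.2 and 5.3.**

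| Step | Referred | Data pull | Control |
|---|---|---|---|
| Chance decides the offer | No | Yes, invitation | Yes, sampled from the uninvited |
| Clinician's decision | Referral | Opt-out at two sites | Opt-outs removed under 5.2; unclear under 5.1.1 |
| Phone screen | Not described | Yes | No |
| Patient accepts; decliners replaced | Not described | Yes | No |
| Agrees to study, HIPAA authorization | Yes | Yes | No (waiver) |

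An intention-to-treat analysis of the one random element would compare invited with uninvited data-pull patients and keep the invited decliners. The plan's scheduled set drops those decliners and adds all enrolled referrals.

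**2. What the covariates can do.** For patient i at time t, write the model as A1c(i,t) = u(i) + a·T(i) + b·t + d·T(i)·t + c·X(i) + error, where T is treatment, X holds the time-constant covariates and d is the difference-in-differences estimate. The within-patient change is b + d·T(i) + error: both u(i) and c·X(i) cancel. With complete data, d is the difference in mean change whatever main effects are added.

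Simulated trials with no true effect (560 per arm; 0, 6 and 12 months; 100 replicates; assumed inputs; site intercept omitted) agree:
- Differential trend of −0.30, complete data: −0.299 without covariates and −0.299 with them, identical in every replicate.
- Same trend, some outcomes missing: main effects moved single data sets by up to about 0.14, but the mean stayed near −0.30.
- Transient baseline elevation of 0.6 on the SMA side: −0.599 with or without main effects, −0.366 with covariate-by-time terms. Those terms help but do not remove the bias.

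**3. The plan's own figures.** Section 5.6.2 gives 560 to 1,568 active patients. These follow from seven sites: 7 × 10 × 8 = 560 and 7 × 16 × 14 = 1,568. It claims power 0.8 for 0.5 A1c points against controls. Inputs from Section 5.6.2 are SD 1.45, group size 8, and ICC 0.10 in SMA groups and 0 in controls. Two-sided alpha 0.05 is my assumption, as none is stated.

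SE = 1.45 × √[(1 + 7 × 0.10)/560 + 1/560] = 1.45 × √(2.7/560) = 0.101.

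Power = Φ(0.5/0.1007 − 1.96) = 0.999, so 0.8 holds as a floor. Precision is not the problem.

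**4. Scale of a trend difference.** With no true effect and an uncorrected trend difference B, the false-positive rate is P(|Z + B/SE| > 1.96).

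| B (A1c points) | ICC 0.10, SE 0.101 | ICC 0, SE 0.087 |
|---|---|---|
| 0.1 | 17% | 21% |
| 0.2 | 51% | 64% |
| 0.3 | 85% | 93% |

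These values of B are assumed. The documents give none for this contrast.

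**5. Whether baseline A1c-by-time adjustment should replace the present model.** Take no effect and no drift, with SMA patients stably 0.3 points higher (assumed), baseline SD 1.5 (assumed) and change SD 1.45. If the variance is equal at both times, 1 − ρ = 1.45²/(2 × 1.5²) = 0.467, where ρ is the correlation between baseline and follow-up. Linear baseline adjustment then has bias of about 0.3 × 0.467 = 0.14, while the present model has none. Simulation gave 0.007 for the present model, 0.086 with a baseline-stratum-by-time term and 0.147 with a linear one. Positive values go against SMAs.

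**The case against.** **Invitation is random.** Sections 5.1.1 and 5.2 say so, and data-pull controls come from the same pool. This stands. A reader might infer that chance plays no part between SMA and usual care; the documents do not support that. The defect is that chance governs invitation only, omits referrals, and is not preserved in the set analysed.

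**The plan condemns its own contrast.** A reader might cite Section 5.1.1: "If patients are then selected differentially into the groups we will lose all the advantages of the randomization step". In context that sentence concerns the randomised sequence of SMA and SMA+P2P groups, and the identical recruitment script follows as the safeguard. It is not a statement about usual care.

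**Referrals bypass eligibility.** A reader might infer this from the separate entry criterion. It replaces only the first item in Section 5.4. The A1c threshold and other criteria still apply, and Section 5.2 limits enrolment to scheduled patients who meet them.

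**The plan already treats the contrast as observational.** Difference-in-differences and propensity matching are tools for that purpose. This stands in part: stable level differences are removed, and matching adds adjustment to the otherwise unadjusted Mann-Whitney tests. But the named score variables include no A1c history, treatment or earlier utilization.

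**The result must favour SMAs.** This cannot be said. Volunteers may improve anyway; referred patients may be harder to control. The documents report no baseline imbalance from which to forecast a bias.

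**Conclusion.** The label in Section 5.6.1 is wrong as written and must be corrected. This rests on the described recruitment steps alone and needs no assumption about bias. The comparison sets enrolled patients scheduled for an SMA against a random sample of eligible uninvited patients; it is non-randomised.

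The adjustment point also holds, more narrowly. With complete data and covariates entered without time interactions, the estimate is the unadjusted difference in change, so differing A1c trends are not corrected. With missing outcomes the identity is no longer exact, but the simulated bias remained on average.

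The rates of 17%, 51% and 85% are a scale, not a forecast: they assume the trend differences, the alpha, and the plan's minimum sample and worst-case ICC. A reader might also conclude that the present model should give way to baseline-by-time adjustment. That does not follow, because each rests on a different assumption and either can mislead.

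**What to change.** 1. **Required.** In Section 5.6.1, replace the intention-to-treat and randomised wording with: *non-randomised comparison of patients scheduled for an SMA (by referral, or by acceptance after random invitation) and enrolled in the study with a random sample of eligible uninvited patients*. Limit the conclusion accordingly. This is a protocol text edit; the cost is a more cautious claim.
2. **Advised.** Keep the present model as primary. Add sensitivity analyses with covariate-by-time terms (baseline A1c, site, baseline SBP, insulin and statin use, prior utilization) and a propensity score that adds these variables to demographics. State that baseline-by-time adjustment rests on a different assumption and can add bias if the groups differ stably in level. Richer 1:1 matching may discard patients, since controls only equal active patients in number. Section 5.5 lists the clinical and utilization data types for controls, but whether the control data request covers pre-baseline values must be checked.
3. **Advised.** As a secondary analysis, report the A1c contrast separately for data-pull and referred patients. The stream shares are unknown. With ICC 0.10, 8 patients per group in the stream and alpha 0.05, an assumed 25% share (140 against 560 controls) gives SE = 1.45 × √(1.7/140 + 1/560) = 0.171 and power 0.83 for 0.5 points; a 50% share (280 against 560) gives 0.97. With controls cut in proportion, power is 0.70 and 0.94.
4. **Advised.** Align the control definition in Section 5.1.1 with Section 5.2, so that patients whom providers opted out are not sampled as controls.

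These steps reduce selection on referral and willingness; they do not remove it.
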